4.3.5. Subgroup and Risk-Adjusted Analyses

Subgroup analyses and analyses that account for differences in baseline risk factors will be performed and will be regarded as exploratory. The subgroup analyses for time-to-event variables will only be conducted if the number of outcomes is at least 50.

4.3.5.1. Prespecified Subgroup Analyses

Subgroup analyses will be performed for the following prespecified subgroup variables:

- gender (female and male)
- age group (age <median, and age ≥median)
- duration of diabetes (duration <5 years, 5 years ≤ duration <10 years and duration ≥10 years)

- body mass index (BMI) (BMI <median and BMI ≥median)
- baseline HbA1C (HbA1C <median and HbA1C ≥median)
- geography (region) (US/Canada, South America, Europe, and Asia Pacific)
- prior CV event (Yes, No)

For the purpose of the subgroup analyses, South Africa will be included in the geographical subgroup of Europe, Australia and New Zealand in the subgroup of Asia Pacific, and Mexico in the subgroup of South America.

A prior CV event is defined as a history of MI, or a history of myocardial ischemia by a stress test or with cardiac imaging, ischemic stroke, coronary, carotid or peripheral artery revascularization, or hospitalization for unstable angina with electrocardiogram (ECG) changes, or need for percutaneous coronary intervention (PCI).

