Demographic and baseline characteristics will be summarized by treatment group. Separate subgroup analyses of the primary endpoint will be performed based on patient demographics and baseline characteristics. Predefined key subgroups include gender, age group (age  $<65$  years and age  $\geq 65$  years), prior CV event, body mass index below and at or above the median, duration of diabetes (0 to 5 years, 5 to 10 years, and 10 or more years), baseline HbA1c below and at or above the median, and geography. Consistency of treatment effects across subgroups will be assessed using an interaction term in the Cox regression model. As the number of these subgroup variables may be large, the probability of observing at least 1 statistically significant result just by chance is nontrivial. Thus, these analyses will be considered exploratory.

For other analyses, including analyses of prespecified safety measures, the number and proportion of patients will be calculated for binary data and summary statistics (mean, median, standard deviation, 10th and 90th percentiles) will be presented for continuous data. Summary statistics of change from baseline for HbA1c per year will be presented along with percentage of patients within ranges of clinical interest (for example, HbA1c  $<7.0\%$ ).

Safety data will be monitored on an ongoing basis. Clear evidence of net harm that is consistent over time and across subgroups would justify early stopping of the trial. One interim and 1 final analysis of the efficacy data will be performed. The interim analysis will occur when approximately 61% (730 events) of the expected number (1200) of primary endpoint events have accrued. The final analysis will occur when approximately 1200 patients have experienced a primary endpoint event if the trial is not stopped early.

The secondary analyses will follow a graphical statistical approach for multiple comparisons to strongly control the overall Type I error rate in the trial at a 2-sided  $\alpha$  level of 0.05.

An IDMC will monitor unblinded study data on a regular basis to assess study progress, efficacy, and patient safety.

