### **12.2.11. Subgroup Analyses**

The effects of dulaglutide and placebo on the incidence of primary endpoint events will be examined across the following subgroups:

- Gender (Female vs. Male)
- Age (Age <65 years, and Age  $\geq$ 65 years)
- Prior CV event
- Duration of diabetes (Duration <5 years, 5 years  $\leq$  Duration <10 years, and Duration  $\geq$ 10 years)
- Body mass index (<median and  $\geq$ median)
- Baseline HbA1c (<median and  $\geq$ median)
- Geography (North America, South America, Europe, Asia, Other)

Forest plots of the hazard ratio will be provided for each subgroup. Other subgroups may be examined if determined to be of interest. As the number of these subgroups may be large, the probability of observing at least 1 statistically significant result just by chance is nontrivial. Thus, these analyses will be considered exploratory. All tests of interactions between treatment and subgroup will be conducted at a 2-sided alpha level of 0.10.

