4.1. Determination of Sample Size

For the initial powering of the trial, a minimum of 1067 unique primary endpoint events will be required to provide 90% power to demonstrate the superiority of dulaglutide over placebo at a true hazard ratio of 0.82 and 2-sided significance level of 0.05. To calculate the sample size, the following assumptions were used and yielded a sample size requirement of approximately 9600 patients: (1) two-sided significance level of 0.05; (2) 90% power for the primary endpoint; (3) patient accrual over 3 years; (4) annual placebo group event rate of 2.0% for the primary endpoint; (5) maximum duration of follow-up of 8 years; (6) a detectable hazard ratio of 0.82 between dulaglutide and placebo in terms of the primary endpoint; and (7) annual dropout rate of 0.15%.

The calculations were performed using nQuery Advisor® Version 7.0. This software provides sample size estimates for tests based on exponential survival, accrual period and dropouts. The sample size and other trial characteristics, such as interim analysis power, were also assessed through trial simulation. Trial assumptions were based on information from the scientific leadership of the study and a review of the relevant literature.

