For subgroup analyses, all tests of interactions between treatment groups and other factors will be conducted at a nominal 2-sided alpha level of 0.10 and will be deemed to be exploratory. No adjustment for multiplicity will be performed unless otherwise specified.

Countries in similar geographic regions with <10 patients will be pooled in order to achieve a pooled country of at least 10 patients. All analyses using country in the model will use pooled country, unless otherwise specified. The final pooling by country and geographic region will be specified prior to data lock.

The baseline is Visit 3. If baseline data are missing, the last measurement taken prior to this visit will be used for the baseline measurement.

The primary analysis and key secondary CV endpoint analyses will be based on adjudicated events that occurred after randomization (Visit 3). Sensitivity analyses may be conducted

including events reported by investigators or events identified through safety reviews, to assess their impact on the primary analysis results.

All analyses will be implemented using SAS Version 8.2® or higher.

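### The Protocol and SAP prespecify different age cuts without explanation, and the SAP tests effect modification by age, BMI and HbA1c only on median splits

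*SAP*

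**What the plan says.** SAP 4.3.5.1 lists the prespecified subgroup variables. Three are cut at the sample median: "age group (age <median, and age ≥median", "body mass index (BMI) (BMI <median and BMI ≥median" and "baseline HbA1C (HbA1C <median and HbA1C ≥median". Diabetes duration has three fixed categories.

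The Protocol agrees on BMI ("body mass index below and at or above the median" in the synopsis, and likewise in 12.2.11) and on HbA1c. It differs on age: the synopsis and 12.2.11 both cut at 65 years ("Age (Age <65 years, and Age" opens the entry in 12.2.11).

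The Protocol synopsis assesses consistency of effect with an interaction term in the Cox model. SAP 4.2 sets the level: "all tests of interactions between treatment groups and other factors will be conducted at a nominal 2-sided alpha level of 0.10". SAP 4.3.5 states the status of the subgroup and risk-adjusted analyses: they "will be performed and will be regarded as exploratory".

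Neither document plans an interaction between treatment and a covariate on its continuous scale. The risk-adjusted models in SAP 4.3.5.2 and 4.13.3 use the subgroup variables as adjustment terms and to define further subgroups, not as treatment interactions.

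The SAP revision history records other subgroup changes (race replaced and later removed, variables regrouped, prior CV event redefined). It has no entry for the age cut.

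**The concern.** There are two issues, and they are independent of each other.

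- **Age cut.** Protocol amendment (d) and SAP Version 4 both carry the 1200-event design, so they were aligned on the main change but not here. Two different age analyses can each be called prespecified. If the matter stays open until results are known, a reader cannot tell which was intended, and an explanation first given then cannot show that the choice came earlier.
- **Sensitivity.** Tests of interaction are weak to begin with. Reducing a continuous modifier to two halves weakens them further when the effect changes gradually. A non-significant interaction is easily read as a consistent effect, so avoidable loss of power matters even in an exploratory analysis.

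**Working it through.** **1. The age texts side by side**

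| Source | Age subgroup | Reason for difference |
|---|---|---|
| Protocol synopsis | below 65 / 65 and over | – |
| Protocol 12.2.11 | below 65 / 65 and over | – |
| SAP 4.3.5.1 | below median / median and over | none given |
| SAP revision history | no entry | none given |

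The two definitions coincide only if the observed median is 65. Neither document gives the median.

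**2. The plan's own figures.** The documents state no power for the interaction tests, so the check starts from the primary test. SAP 4.1 says "a minimum of 1067 unique primary endpoint events will be required to provide 90% power" at a hazard ratio of 0.82 and two-sided alpha 0.05. With 1:1 allocation, Schoenfeld's formula gives D = 4(1.960 + 1.282)² / (ln 0.82)² ≈ 1067, or 1068 when rounded up. A two-look O'Brien-Fleming spending function at 730 of 1200 events gives an interim alpha of 0.0081, a final alpha of 0.0474 (Protocol 0.0475, SAP 0.048) and overall power of 92.8%, as stated.

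**3. Information kept by a split.** If the log hazard ratio is linear in a modifier X, replacing X by the indicator of X ≥ cut keeps a fraction R = corr(X, indicator)². For a normal X cut at its median, the covariance in SD units is 1/√(2π) = 0.399 and the indicator's variance is 1/4, so R = 0.399² / 0.25 = 2/π = 0.637. The loss is 36%. At 1200 events the split behaves like 1200 × 0.637 ≈ 764 events, and matching the continuous test would take 1200 × π/2 ≈ 1885.

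**4. Power of the interaction test.** Power ≈ Φ(|b|√(D·R/4) − 1.645), plus a negligible opposite tail. Here D = 1200, two-sided alpha is 0.10, and b is the change in log hazard ratio per SD of X. The slope that gives 80% on the continuous scale is (1.645 + 0.842)/√300 = 0.144.

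| Slope per SD | Continuous | Median split |
|---|---|---|
| 0.05 | 22.4% | 18.0% |
| 0.10 | 53.5% | 39.8% |
| 0.144 | 80.0% | 63.3% |
| 0.20 | 96.6% | 86.8% |

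Starting from 90%: Φ(0.798 × (1.645 + 1.282) − 1.645) = Φ(0.690) = 75.5%, where 0.798 = √0.637.

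**5. Sensitivity to the shape of X.** The documents give no covariate distributions, so these are assumptions.

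| Assumed modifier | Loss |
|---|---|
| Uniform | 25% |
| HbA1c, normal truncated at 9.5% | 32–33% |
| BMI, normal truncated at 23 | 34% |
| Age, normal truncated at 50 | 34–36% |
| Normal | 36% |
| Lognormal (log-SD 0.5) | 48% |
| Exponential | 52% |

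If the effect stepped exactly at the median, nothing would be lost.

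**6. The 65-year cut.** With assumed mean ages of 60 to 68 and SDs of 6 or 8, cutting at 65 keeps 55% to 66% of the information, against 64% to 66% for the median. Changing the cut does not recover the loss.

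**7. Simulation.** A Cox simulation of 400 trials of 9600 patients (hazard ratio 0.85 at the mean, slope 0.1436 per SD, about 1125 events) gave R = 0.63, with power of 79% continuous and 57.5% split. The formula at 1125 events gives 77.7% and 60.9%, within simulation error.

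**The case against.** The strongest case on the other side is that the median splits are a choice of method. For BMI and HbA1c the two documents agree, the analyses are labelled exploratory throughout, and no claim, alpha or stopping rule rests on them. The Protocol also allows further exploratory analyses. The large power gap needs strong effect modification: around a hazard ratio of 0.85, a slope of 0.144 means about 0.74 at one SD on one side of the mean and 0.98 on the other. At a slope of 0.05 both tests are weak. Spline terms also use degrees of freedom that the comparison ignores. All of this stands. It limits the importance of the point but does not remove it.

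A reader might infer three stronger things that the documents do not support.

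- **That Protocol 12.2.1 was breached.** That section lets a changed method and its justification be described in the SAP and/or the study report. The SAP states its cut, its change log claims only to list key changes, and a reason could still be given in the report.
- **That the median is a cut chosen to suit the results.** A pooled baseline median depends on neither outcome nor arm. The amendment (d) summary says enrollment was already complete, and SAP Version 4 was to be approved before the interim analysis. Nothing shows that either cut favors a result.
- **That a non-significant interaction is defined as proof of consistency.** Neither document says so. The risk lies in how it will be read.

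**Conclusion.** Both parts hold, at low severity.

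The age conflict is plain in current text and unexplained. The fact that the SAP is the later and more detailed analysis document suggests that its cut would operate, but nothing states that it replaces the Protocol's.

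The information loss of about a third rests on two assumptions: a log hazard ratio close to linear in the modifier, and a roughly symmetric modifier. For BMI and HbA1c this is an efficiency weakness shared by both documents, not an inconsistency. For age, testing only at the median describes the SAP alone.

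The effect is confined to exploratory subgroup inference. The primary test, its alpha and its power are unaffected, and the event figures in the working express efficiency; they are not a case for enlarging the trial.

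**What to change.** Before unblinding:

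1. In SAP 4.3.5.1, use the Protocol's 65-year cut for age, or keep the median and record the change with its reason.
2. Keep the prespecified categorical interaction tests and forest plots. Reducing the categories to display only would drop tests that the Protocol specifies and open a new gap between the documents.
3. Beside them, add for age, BMI and HbA1c a Cox model with treatment, the continuous covariate and their product, plus a spline check for nonlinearity. Diabetes duration, which has three categories and is not median-split, could be included.

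Steps 1 and 3 are both needed: settling the age cut removes the conflict but recovers none of the lost information. The cost is a few lines of SAP text, a few more exploratory fits and a linearity assumption that the spline check examines. Design, data collection and patient care do not change.

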4.3.5.2. Exploratory Subgroup Analyses

To select additional factors for subgroup analyses, clinically relevant baseline characteristics will be identified for the primary outcome variable and each of its components. A Cox proportional hazards regression model adjusted for baseline risk factors will be obtained using a model selection process, guided by clinical review of the published literature. All these factors will be forced into the model, along with the above prespecified subgroup variables. For all factors, the significance level for remaining in the model will be 0.05. After the selection of terms into the model concludes, treatment will be added to the model. For all dichotomous terms in the final model, parameter estimates, standard errors and p-values plus the hazard ratio and its 95% CI will be reported.

Any factors remaining in the final proportional hazards model will also be used for subgroup analyses.

4.3.6. Multiple Comparisons/Multiplicity Adjustments

The primary objective of this study is to demonstrate with statistical significance a clinically meaningful reduction in the incidence of primary endpoint events. There will be 1 interim analysis and 1 final analysis. The interim analysis will be performed when approximately 61% (730) of the primary endpoint events have occurred and have been adjudicated as such. The final analysis will be performed at 100% of the total information (approximately 1200 adjudicated primary endpoint events) if the study is not stopped early. Appropriate adjustments for multiplicity will be made to maintain an overall type I error rate of <0.05 (Section 4).

Multiplicity adjustments will be performed for the analyses on the primary and secondary efficacy endpoints in order to control the overall Type I error rate at a 2-sided alpha level of 0.05. For repeated testing of the primary outcome via interim analysis, an O'Brien-Fleming alpha spending function will be used to control alpha across the interim and final analyses for the testing of the primary endpoint (GBDJ Protocol Section 12.2.2). A graphical approach will be

used to control the type I error rate across the secondary endpoint analyses at the final analysis time point or at the interim analysis time-point if the decision is to stop the trial following the interim analysis (GBDJ Protocol Section 12.2.2 and Section 12.2.12 for the Interim Decision Rule).

4.3.6.1. Graphical Approach

A graphical approach using a sequentially rejective Bonferonni multiple-testing procedure to control the family wise error rate (FWER) will be used for the secondary hypotheses in this study. In general, a graphical approach is characterized by prespecifying:

- the hypotheses (or nodes) within the testing algorithm
- an initial allocation of α
- weights along the lines (edges) that connect the hypotheses tests.

The initial allocation of α is such that the sum of all α is the full alpha available for the analyses. The algorithm begins by testing all hypotheses that have α allocated to them. If any hypothesis is rejected then the graph is updated to reflect the reallocation of α where the proportion of α reallocated to other hypotheses is determined by the weights along the edges. Hence the α can be considered “recycled” as described by Bretz and colleagues (2009) as long as at least one hypothesis is rejected. This iterative process of updating the graph and reallocating the α is repeated until no further hypotheses can be tested.

[figure not shown]
Figure GBDJ.4.2 shows the primary and secondary endpoints, the α allocation, and associated weights for the REWIND Study. Only the hypothesis test for the primary endpoint (Composite MACE) is initially allocated the full value of α at the given analysis time-point (for example, at the final analysis time-point with 1200 events, $\alpha = 0.048$, 2-sided); all other hypotheses are allocated $\alpha=0$. Additionally the weights are provided along the edges.

The first hypothesis tested will be for the primary endpoint (time to first composite MACE) which is tested at the alpha value used for the primary analysis at the given analysis time point. If that hypothesis is rejected then the graph is updated and the hypotheses for the following 3 endpoints will be tested with an α based on the weights indicated by the 3 edges (arrows) coming from the Composite MACE. Figure GBDJ.4.3 demonstrates what the graph would look like if the first test (Composite MACE primary endpoint) is rejected at the final analysis time-point with 1200 events, with α reallocated as follows:

- Time to first Nonfatal MI has a weight of 0.15 resulting in $\alpha = (0.048*0.15) = 0.0072$
- Time to CV Death has a weight of 0.7 resulting in $\alpha = (0.048*0.7) = 0.0336$
- Time to first Nonfatal Stroke has a weight of 0.15 resulting in $\alpha = (0.048*0.15) = 0.0072$.

[figure not shown]
If any of the 3 hypotheses above are rejected, the graph is again updated and its alpha is reallocated to the subsequent tests according to the weights given in the figure. It should be noted it is possible for the hypothesis for a particular endpoint to fail to be rejected the first time it is tested, but subsequently receive enough α from successfully rejected hypotheses and be rejected the second time it is tested. This iterative process of updating the graph and redistribution of α is continued until no further hypotheses can be tested.

The graphical approach to multiplicity control has been evaluated in several peer reviewed publications: Bretz and colleagues (2009), Bretz and colleagues (2011); and Alosch and colleagues (2014). Because graphical approaches are closed testing procedures, they control the FWER strongly (Alosch et al. 2014). This closed testing system controls the FWER to ≤ 0.05 .

Abbreviations: A-C Mortality = all-cause mortality; CV = cardiovascular; HUA = hospitalization for unstable angina; MACE = major adverse cardiovascular event; MI = myocardial infarction.

Figure GBDJ.4.2. The graphical approach with initial α allocation and weights at the final analysis time point with 1200 primary MACE events.

Abbreviations: A-C Mortality = all-cause mortality; CV = cardiovascular; HUA = hospitalization for unstable angina; MACE = major adverse cardiovascular event; MI = myocardial infarction.

Figure GBDJ.4.3. The graphical approach reflecting α propagation after rejecting the first hypothesis at the final analysis time point with 1200 primary MACE events.

No adjustments will be made for multiple comparisons on other endpoints.

4.3.6.2. Interim Analysis and Control of Type I Error following an Efficacy Stop Decision

4.3.6.2.1. Data Cut-off Date for the Interim Analysis

The interim analysis is planned to be conducted when a minimum of 730 positively adjudicated MACE endpoints events have occurred. It is expected that there will be more than 730 events in the pool for the interim analysis, as all events that are adjudicated on the same day as the 730th positive event will also be included in the analysis. The data cut-off date for the interim analysis will be the event date, from the adjudicator's opinion, of the most recent event in this pool of unique subjects with positively adjudicated primary MACE endpoint events. In addition, all efforts will be made to adjudicate the majority of all MACE events with events dates prior to this cut-off date, and these adjudicated events will be included in the interim analysis (Figure GBDJ.4.4).

At the interim analysis, the alpha level used for the analysis will be determined based on the actual number of events included in the analysis using EAST Software (EAST 6, Cytel, www.cytel.com). If the trial continues to the end following an IDMC review of the interim

results, the final alpha will be adjusted based on the final number of primary MACE events using EAST software. If the IDMC recommends stopping the trial for efficacy following the interim analysis, analyses will be performed on this post-interim, final-lock database using the adjusted significance level alpha based on the Whitehead procedure (Section 4.3.6.2.2).

[figure not shown]

Figure GBDJ.4.4. Example of data cut-off date for the analysis of the primary MACE events.

4.3.6.2.2. Controlling Type I Error across Interim and Final Analyses Following Early Termination for Efficacy

All events until study closure will be collected and analyzed as part of the conduct of the study following a decision to stop the study early for efficacy. This post-interim, final-lock dataset will be comprised of all events, including those events collected after the interim stopping decision until final trial closure. These data are valuable in the full interpretation of the conduct of the study and will be included in the submission to Food and Drug Administration (FDA). If the study is stopped at the interim as a result of meeting the interim boundary, the interim analysis data used for making the decision will be included as part of the Common Technical Document (CTD). The post-interim final lock dataset will be the primary database to be used to support safety and efficacy in the CTD and for proposed labeling. While the Type I error rate at interim is already controlled at the interim lock, in order to control for Type I error for the post-interim final analysis, Whitehead's approach will be used to recalculate the rejection boundaries since the additional events after the interim will be included in the primary dataset (Whitehead1992). Both the interim and post-interim final data (primary and key secondary endpoints) will be included in the CTD and the CSR for efficacy.

The following is an example of the use of Whitehead's approach in the context described above. For example, with 730 events at the interim lock, the one-sided p-value boundary is 0.004. If the interim p-value is less than the stopping boundary, then the trial may be stopped early for

efficacy. If the trial is stopped early for efficacy, additional events will accrue between the interim lock and the post-interim final lock and this could range between 100 to 250 additional events. Whitehead's approach controls Type I error by recomputing the final p-value boundary based on the number of events included in the interim lock plus the additional events accrued. For example, with an additional 250 events following the interim lock (for a total of 980 events), the one-sided p-value boundary for the primary analysis is 0.013. Using Whitehead's approach, at the post-interim final analysis (following trial stop), the stopping boundary will be calculated based on the total number of primary MACE events included in the post-interim final lock (out of the 1200 events planned for the end of the trial) using the protocol-specified O'Brien-Fleming spending function. If the trial does not stop early for efficacy, Whitehead's approach will not be used.

